**Title: Testing a Brief Substance Misuse Preventative Intervention for Parents/Guardians of
5th-7th Grade Students**

NCT Number: NCT03925220

Study Protocol

Document Date: August 10, 2023; Revised: November 11, 2018

1.0 Purpose of the study:

The purpose of this study is to test the efficacy of a brief, communication-based, substance use preventive intervention for parents of pre/early adolescents. A parallel-group randomized controlled trial (RCT) to test the primary hypotheses that, relative to parents in the comparison condition, parents receiving the intervention, over the study period, will have, on average: 1) greater quality of interactions at meals, 2) a greater number of conversations about substances, and 3) higher quality of content in their conversations with their children about substance use. A companion primary hypothesis will be tested to determine if children of parents randomized to the intervention have fewer intentions and reduced willingness to use substances, reduced affiliation with substance-using peers, and increased negative attitudes and expectancies about substance use in contrast to children of parents in the comparison condition at study follow-up. We will also test a secondary aim's hypothesis, that children of parents assigned to the intervention condition will have a delayed initiation of substance use compared to the comparison condition.

2.0 Background / Literature Review / Rationale for the study:

Universal, family-based substance use preventive interventions have been shown to be efficacious, but programs that have been most effective are resource intensive and require extensive time and effort for program staff and participants. Therefore, an approach to universal substance misuse prevention is needed that is effective, resource-efficient, able to be disseminated easily, and sustainable.

3.0 Participant Population:

PHASE 1:

We propose to enroll parents of pre/early-adolescents (grades 5-7) with their child who live and attend school in Massachusetts.

Inclusion criteria include: 1) the parent must have a child between 5th-7th grades at the start of the project; 2) the parent must be the custodial parent, living with the child at least 50% of the time (as in the case of joint custody); and 3) parental consent and child assent are obtained. If a parent has more than one child that meets these criteria, the target child to participate in the intervention will be randomly chosen by research staff.

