5.2 Sample Size

PHASE 1:

The number of participants from each school will depend upon the number willing and available to participate in each school district, and the total number of participants from all sites combined shall not exceed 1500 (750 parent/child dyads). Note: Sometimes

participants are referred to as parent/child dyads in participant facing materials, but all verbal communication clarifies that a parent/child dyad or pair consists of 2 participants.

PHASE 2:

We will not recruit any new participants for this portion of the study.

Procedures Involved:

PHASE 1:

Eligible, consenting parents and their assenting child will complete baseline assessments related to their family practice of eating meals together, communication skills, parenting styles, and their own substance use. Parents will then be randomly assigned to one of two conditions: 1) intervention, or 2) comparison. Parents and children will then be followed at four follow-up points at 3, 6, 12, and 18 months.

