**Aim 1:** To determine the efficacy of the brief intervention on parent outcomes. The proportion of parents who more frequently communicate will be compared between conditions across the follow-up periods using a repeated measures log-binomial regression analysis (via generalized estimating equations; GEE), with an appropriate covariance structure and adjusting for baseline scores. Covariates will be added to the modeled analyses if differences among baseline characteristics are observed. A test for interaction between condition and follow-up point using the above models will assess whether there is a differential intervention effect across time, taking intervention dose delivered and received into account. To assess quality of mealtime interactions, we will first score the videos according to the IFIRS and then analyze the data using repeated measures analysis of covariance (i.e., a linear mixed model) to compare the two conditions across the follow-ups, using an appropriate covariance structure and adjusting for baseline scores. A similar analysis will be used for the summed scores from the FAsTask, which assess the quality of parent-child conversations about SU.

**Aim 2:** To examine the effects of the intervention on child SU beliefs, intentions, and willingness, and affiliation with substance-using peers. We will compare the proportion of children with intentions and willingness to use substances, negative SU attitudes and expectancies, and substance-using peers between conditions across the follow-up periods using a repeated measures log-binomial regression analysis (via GEE), with an appropriate covariance structure and adjusting for baseline scores.

**Secondary Aim 1:** To examine the effects of the intervention on SU initiation. To assess whether children of parents in the intervention condition delay the initiation of SU longer than the comparison condition, we will compare the incidence of initiation using a

discrete-time survival analysis via a complementary log-log regression model, as the date of initiation between follow-up time points may not be known exactly.

Exploratory analyses will be run by race and ethnicity. Because it is known that subgroup analyses have less statistical power than the primary analysis, we will conduct exploratory analyses to determine whether the efficacy of the intervention varies by race and ethnicity, to inform future adaptations.

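### SAP Aim 2 tests negative attitudes and expectancies only as a yes/no proportion with no stated cut-point, although the hypothesis reads most naturally as one of degree; under most plausible cuts this loses power

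*SAP*

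**What the plan says.** Protocol section 1.0 states a companion primary hypothesis for the children: relative to the comparison arm they will "have fewer intentions and reduced willingness to use substances, reduced affiliation with substance-using peers, and increased negative attitudes and expectancies about substance use".

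SAP Aim 2 sets the test: "We will compare the proportion of children with intentions and willingness to use substances, negative SU attitudes and expectancies, and substance-using peers", with the arms compared by log-binomial regression fitted by GEE and adjusted for baseline scores. That model needs a 0/1 outcome at each follow-up. The SAP text supplied gives no threshold for classing a child as having negative attitudes or expectancies, no reason for dichotomising, and no supporting analysis on the original scale.

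SAP Aim 1 treats its two quality outcomes differently. For the coded meal videos the plan is to "analyze the data using repeated measures analysis of covariance (i.e., a linear mixed model) to compare the two conditions across the follow-ups". For the conversation task, "A similar analysis will be used for the summed scores from the FAsTask".

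**The concern.** Stronger negative attitudes and expectancies are most naturally a matter of degree. Under Aim 2, a child who moves from mildly to strongly negative contributes nothing unless that move crosses the cut. The programme could do what section 1.0 predicts and still be reported as having no effect on these outcomes.

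The sample makes this more pressing. The trial enrols families of 5th to 7th graders through a universal approach, so many children may already hold negative views at baseline. The documents do not give that share. If it is high, a proportion has little room to rise while a score may still move. And because the cut is unstated, it could be chosen after the data are seen.

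**Working it through.** The documents give no effect size, alpha, target power, prevalence or scale for Aim 2, so there is no planned figure to reproduce. The question is how much power a yes/no version gives up, and when.

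**Inputs from the documents.** Enrolment "shall not exceed 1500 (750 parent/child dyads"), two arms, and follow-up at 3, 6, 12 and 18 months (protocol section 5.2).

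**Assumed inputs.** 1:1 allocation, two-sided 5%, and a shift of d = 0.20 SD in the underlying trait.

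**Step 1: closed form, one time point, 750/2 = 375 per arm.**

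Score: power = Φ(d√(n/2) − 1.96) = Φ(0.20 × √187.5 − 1.96) = Φ(0.779) = 0.78. Number per arm for 80% power: 2 × (1.96 + 0.842)² / 0.20² = 393.

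Yes/no: if a share p₁ of comparison children lie beyond the cut, the same shift gives p₂ = Φ(Φ⁻¹(p₁) + d). At p₁ = 0.90, p₂ = Φ(1.282 + 0.20) = 0.931. The power of a two-proportion test is then Φ{[(p₂ − p₁)√n − 1.96√(2p̄q̄)] / √(p₁q₁ + p₂q₂)} = 0.33, where p̄ is the mean of p₁ and p₂ and each q = 1 − p.

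| Comparison children beyond the cut | p₂ | Power, yes/no | n per arm for 80% | Ratio to 393 |
|---|---|---|---|---|
| 50% | 0.579 | 0.59 | 620 | 1.6 |
| 70% | 0.766 | 0.53 | 714 | 1.8 |
| 80% | 0.851 | 0.46 | 861 | 2.2 |
| 90% | 0.931 | 0.33 | 1284 | 3.3 |
| 95% | 0.968 | 0.22 | 2034 | 5.2 |

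Even the most favourable cut, at the median, costs about 20 points of power. This treats the score as normal and free of ceiling effects.

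**Step 2: simulation with repeated measures and ordinal items.** Further assumptions: 85% retained (750 × 0.85 = 637.5, taken as 638, or 319 per arm), four follow-ups, within-child correlation 0.5, and four 5-point items with loading 0.7. Each child's follow-up mean is regressed on arm and baseline value with robust standard errors, once for the score and once for the yes/no version. The rows come from separate runs with different item cut-points.

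| Attitudes/expectancies, d = 0.20 | Score | Yes/no |
|---|---|---|
| Cut near the median | 0.93 | 0.81 |
| 86% already negative | 0.93 | 0.64 |
| 92% already negative | 0.92 | 0.51 |
| 94% already negative | 0.88 | 0.48 |
| Near-top cut | 0.80 | 0.67 |
| Ceiling-heavy items, top-category cut, 62% positive | 0.75 | 0.74 |
| Ceiling-heavy items, top-category cut, 81% positive | 0.59 | 0.65 |

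At d = 0.15 the pair is 0.70 against 0.32 with 92% already negative, and 0.70 against 0.51 with 75%.

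**Step 3: the other Aim 2 outcomes, same model, d = 0.20.**

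| Outcome and share with the attribute | Score | Yes/no |
|---|---|---|
| Using peers, 60% | 0.86 | 0.77 |
| Using peers, 47% | 0.80 | 0.77 |
| Using peers, 29% | 0.68 | 0.70 |
| Using peers, 16% | 0.57 | 0.61 |
| Intentions/willingness, 38% | 0.76 | 0.75 |
| Intentions/willingness, 16% | 0.55 | 0.60 |

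A separate check used negative-binomial counts of using friends (375 per arm, rate ratio 0.7, dispersion k = 1). Count against any/none gave 0.91 against 0.69 at a mean of 1 friend, 0.61 against 0.49 at a mean of 0.3, and 0.28 against 0.26 at a mean of 0.1. The gap narrows as using friends become rare.

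**The case against.** Section 1.0 fixes a direction between the arms, not a metric. A higher proportion of children with negative attitudes is one legitimate way to test it. The parent hypotheses there are framed as averages; the child sentence is not. This stands. A reader might infer that the two documents define the endpoint in contradictory ways, and the text does not support that.

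A reader might also extend the point to peers, since "reduced affiliation with substance-using peers, and increased negative attitudes and expectancies about substance use" puts them in the same phrase. The wording alone cannot separate them, because intentions and willingness are worded in graded terms too. The peer advantage depends on how common using peers are: in the item-score model it disappears or slightly reverses at 29% and below. The documents give no prevalence, so a change of primary analysis for peers is not supported.

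The attitude items are not described in the supplied text, so the four 5-point items are an assumption. Aim 2's adjustment for baseline scores suggests graded measures, but Aim 1 uses the same phrase for its yes/no communication outcome, so it proves nothing. Step 2 also uses a linear regression as a stand-in for the planned log-binomial GEE. These objections limit how precisely the loss can be stated. They do not remove the missing cut-point or the lack of any score analysis.

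Finally, Aim 1 also analyses communication frequency as a proportion, so the SAP does not use scores uniformly even there. That is true, but it does not justify the choice in Aim 2.

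**Conclusion.** The point holds for negative attitudes and expectancies. The hypothesis is most naturally one of degree, the only planned test is yes/no, and the cut is unstated. Under most plausible cuts power falls: with 319 per arm, four follow-ups and 0.20 SD, from roughly 0.93 to 0.81 near the median, and from about 0.9 to 0.5 when more than 90% of comparison children are already classed as negative. Changes that cross the cut do count, so the outcome is coarse rather than blind.

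The size rests on assumed retention, correlation, scale, effect and prevalence. It should not be read as this trial's actual loss, which may be small for a top-category cut on ceiling-heavy items. For intentions and willingness the simulated yes/no version loses little or nothing. For peers the same holds when prevalence is low. Since this is part of a primary hypothesis, the change should be made.

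**What to change.** In SAP Aim 2:

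- Make the between-arm difference in scale score the primary analysis for negative attitudes and for negative expectancies. Use a baseline-adjusted repeated-measures model with robust standard errors, in line with the Aim 1 quality scores.
- Keep the proportion for these two as a supportive analysis, with its cut-point stated in advance.
- Keep the proportion as primary for intentions, willingness and substance-using peers, and add the peer score or count as a supportive analysis.

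If the attitude and expectancy measures are graded scales, the cost is SAP wording only, with no new visits or participants. The sponsor should confirm that they are, and that the shortened survey described under Compensation (about a tenth of full length) carries the items. A mean score difference is harder to communicate than a risk ratio; the supportive proportion covers that.

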**NCT Number: NCT03925220**

**Statistical Analysis Plan**

**Document Date: August 10, 2023; Revised: November 11, 2018**

## **Data Analysis Plan**

The scientific rigor of this application is reflected in our preliminary analyses, missing data detection and correction procedures, and our data analytic strategies. First, all forms will be checked for missing data and outliers prior to data entry. Attrition effects will be evaluated by testing whether systematic differences exist between participants who complete the research versus those who drop out. We will also examine any pre-existing differences between the two conditions in demographic composition and all measures collected at baseline. Pre-existing group differences in these variables will be accounted for in subsequent analyses, using baseline scores as covariates. Participants will be included in the analysis if they are randomized (i.e., intention -to-treat).

Participants who are lost to follow-up or drop out can affect the validity of the group comparisons if: 1) the outcome of interest is related to being lost or dropped, and 2) it is differential between groups. The missing data mechanism will be formally tested to determine whether it is Missing Completely at Random (MCAR) or Missing at Random (MAR). For completeness in assessing the effect of missingness, two additional analyses will be conducted: 1) a 'per-protocol' analysis among participants who complete all follow-up surveys; and 2) multiple imputation of five data sets using a discriminant function for binary outcomes and Markov chain Monte Carlo for continuous outcomes, assuming the missing data mechanism is MAR.

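### The substance-use initiation model (Secondary Aim 1) fixes no baseline covariate in advance, so what it adjusts for depends on chance imbalance and not on prognostic value

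*SAP*

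**What the plan says.** The SAP (Data Analysis Plan, Secondary Aim 1) compares initiation by a "discrete-time survival analysis via a complementary log-log regression model, as the date of initiation between follow-up time points may not be known exactly". That paragraph mentions no covariate.

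The other efficacy models each have a fixed adjustment:

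- The Aim 1 communication model and the Aim 2 models are log-binomial GEE analyses "with an appropriate covariance structure and adjusting for baseline scores".
- The mealtime-quality (IFIRS) model is a linear mixed model "to compare the two conditions across the follow-ups, using an appropriate covariance structure and adjusting for baseline scores". The FAsTask scores are to be analysed in a similar way.
- In Aim 1 a conditional rule is added on top: "Covariates will be added to the modeled analyses if differences among baseline characteristics are observed".

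A general rule stands before all the aims. The SAP first announces a screen: "We will also examine any pre-existing differences between the two conditions in demographic composition and all measures collected at baseline". It then states: "Pre-existing group differences in these variables will be accounted for in subsequent analyses, using baseline scores as covariates". This is not limited to Aims 1 and 2, so it also covers Secondary Aim 1. The SAP gives no criterion for what counts as a difference.

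On available covariates, the protocol (3.0 Participant Population, Phase 1) requires that "the parent must have a child between 5th-7th grades at the start of the project", so grade is known for every child. Baseline assessments for parent and child cover, among other topics, "communication skills, parenting styles, and their own substance use" (Procedures Involved, Phase 1). Baseline intentions, willingness and peer use must also exist, because Aim 2 adjusts for them.

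**The concern.** For Aims 1 and 2 at least one prognostic covariate stays in the model whatever the baseline screen finds. For initiation nothing is fixed, so the whole covariate set follows from observed differences between arms.

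Under randomisation such differences are chance, and chance imbalance says nothing about how well a variable predicts initiation. Grade or baseline willingness could be left out because it is balanced, while a weak variable enters because it is not. The final model, and whether its hazard ratio is marginal or conditional, would be known only after the baseline data are examined.

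At stake are prespecification and some power, in the only SAP analysis of whether children start using substances. Aim 2 covers beliefs, intentions, willingness and peers.

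**Working it through.** **No planned figure to reproduce.** The documents give no alpha, power, effect size, initiation rate, dropout or covariate strength for this aim. The only sample figure is the enrolment cap: 1500 participants / 2 = 750 dyads. That is a ceiling, not a powered sample size.

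**What the imbalance rule does.** Suppose a difference means p < 0.05 (an assumption). Under randomisation each baseline variable is then flagged with probability about 0.05, whatever its link to initiation. A strong predictor such as grade would be left out with probability about 1 - 0.05 = 0.95.

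**Simulation A: the SAP's model with and without one baseline score.**

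- From the protocol: 750 dyads; four intervals ending at 3, 6, 12 and 18 months.
- Assumed: 1:1 allocation (375 per arm), no dropout, two-sided 0.05, true conditional hazard ratio (HR) 0.60, constant hazard over 18 months, one standard-normal score x with log-HR g per SD.
- Comparison-arm 18-month initiation p fixes the cumulative hazard H through p = E[1 - exp(-H·exp(g·x))].
- Models for child i in interval j: cloglog(h_ij) = a_j + b·condition_i (unadjusted), or with g·x_i added (adjusted). The test is |b/SE| > 1.96, with 1500 replicates per row.

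| Initiation p | Mean events | g per SD | HR unadj. | HR adj. | Power unadj. | Power adj. | Gain (points) |
|---|---|---|---|---|---|---|---|
| 5% | 30 | 0.5 | 0.587 | 0.585 | 25.5% | 26.1% | 0.6 |
| 5% | 30 | 1.0 | 0.592 | 0.581 | 27.1% | 28.1% | 1.0 |
| 10% | 61 | 0.5 | 0.597 | 0.594 | 47.2% | 48.9% | 1.7 |
| 10% | 61 | 1.0 | 0.611 | 0.593 | 45.4% | 50.0% | 4.6 |
| 20% | 122 | 0.5 | 0.605 | 0.598 | 75.8% | 78.5% | 2.7 |
| 20% | 124 | 1.0 | 0.636 | 0.599 | 70.3% | 80.6% | 10.3 |
| 30% | 187 | 0.5 | 0.608 | 0.596 | 91.3% | 93.2% | 1.9 |
| 30% | 190 | 1.0 | 0.644 | 0.597 | 84.4% | 93.3% | 8.9 |

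Monte Carlo error of a single power near 50% is sqrt(0.25/1500) = 1.3 points. The two models were fitted to the same data sets, so their difference is more precise than that. A log-HR of 0.5 is an HR of exp(0.5) = 1.65 per SD; 1.0 is exp(1.0) = 2.72 per SD, which is strong.

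With true HR = 1 and g = 0.8, rejection was 4.5% unadjusted against 4.7% adjusted (p = 10%), and 3.9% against 3.8% (p = 30%).

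With 100,000 dyads and g = 1.0, the unadjusted HR was 0.635 against 0.603 adjusted (p = 20%), and 0.644 against 0.597 (p = 30%). The shift is therefore a property of the two models, not a small-sample effect.

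**Simulation B: grade plus a composite score.** Assumed: 375 per arm, HR 0.65, hazard doubling per grade, composite HR of 1.0, 1.65 or 2.0 per SD, 18-month initiation 13-25%, 700 replicates. Effective sample gain = (mean adjusted z / mean unadjusted z)² - 1.

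| Power unadj. | Power adj. | Gain (points) | Effective sample gain |
|---|---|---|---|
| 53% (grade only) | 55% | 2 | 4.3% |
| 58% | 62% | 4 | 9.0% |
| 54% | 64% | 10 | 17.3% |
| 75% (hazards raised 1.8-fold) | 87% | 12 | 27.8% |

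The mean unadjusted HR was at most 0.68, against 0.64-0.65 adjusted. Type I error was about 4-6% in both models.

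**Simulation C: several covariates entered separately, few events.** Assumed: 750 dyads, HR 0.65, categorical grade plus four predictors, total predictor strength HR 1.65 or 2.0 per SD, 1000 replicates.

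- About 27 events: power 15% unadjusted against 15% adjusted, and 16% against 18%.
- About 52 events: 30% against 32%, and 30% against 33%.
- At about 27 events, up to 17 of 1000 fits did not converge.

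**The case against.** The strongest reply is that the SAP already handles this. The general rule applies to all later analyses, so a reader who infers that the initiation model has no baseline adjustment at all, or is restricted to condition and time, goes beyond the text. That reply stands against the stronger reading. It does not answer the narrower point, because the rule is triggered by imbalance and fixes nothing in advance.

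Second, the contrast with Aims 1 and 2 is not like for like. Those models adjust for the baseline value of their own outcome, and initiation has none. This explains why the usual phrase is missing; it does not justify leaving the covariates open.

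Third, a reader might infer that the trial collects the strongest predictors of initiation and that power is certainly lost. The documents rank no predictor, and all covariate strengths above are assumptions. With rare initiation or weak predictors the gain is close to nil. It is also tempting to argue that the loss matters most because events will be few. The simulations show the reverse: the gain shrinks with few events, and adjustment does not rescue an underpowered comparison.

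Fourth, a reader might call the shift toward 1 a bias. It is non-collapsibility: the condition-only model estimates a valid marginal hazard ratio, and its test keeps its level.

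Finally, a long covariate list is fragile with few events, as the non-converging fits in simulation C show. That stands and limits the fix.

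**Conclusion.** The point holds in a limited form. Secondary Aim 1 is the only efficacy model without a prespecified baseline covariate, and the rule that would supply covariates selects on chance imbalance instead of prognostic value. A short fixed list of variables already collected is a better method: in all three simulations power with adjustment was, apart from simulation noise, equal or higher, and type I error was unchanged where it was tested.

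The size is uncertain: about 0-5 points of power at 5-10% initiation by 18 months, and up to about 10-12 points at roughly 20-30% with strong predictors. These figures assume enrolment to the cap, 1:1 allocation, no dropout in simulation A, and HR 0.60-0.65; none of the rates or effect sizes comes from the documents. Fewer dyads or dropout would lower power in both models. Phase 2 surveys also ask about initiation for up to two more years. The SAP does not say whether they enter this model; if they do, cumulative initiation moves toward the range where the gain is larger.

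The validity of the test is not in question. The change is worth making because it settles the model and the estimand in advance at little cost.

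**What to change.** Add to Secondary Aim 1, before initiation is examined by arm:

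> The complementary log-log model will include condition, follow-up interval, child's grade at baseline, one baseline intentions/willingness score and baseline peer use, regardless of observed balance. For this model the list replaces the rule that adds covariates when the arms differ. The hazard ratio is conditional on these covariates. A model with condition and interval only will be reported as a sensitivity analysis.

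Parent substance use at baseline can be added if events allow. The parameter count shows why the list should stay short: four interval terms + 1 for condition + 2 for grade in three categories + 1 + 1 = 9, or 10 with parent use. At about 30 events that is 30/9 = 3.3 events per parameter; at about 122 it is 122/9 = 13.6.

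The SAP should also say how the score is coded, how missing baseline values are handled, and which children are at risk, since it does not address a child who has already used a substance at baseline.

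The cost is a few lines of SAP text and no new data collection. The downside is that the headline hazard ratio becomes conditional on the covariates; the condition-only sensitivity analysis supplies the marginal one.
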